5.6.4 Exploratory Analyses

Not applicable

5.7 Analysis of Safety

5.7.1 Adverse Events

Adverse events will be coded using the Medical Dictionary for Regulatory Activities (MedDRA) central coding dictionary, version 13.1 or higher, and will be tabulated by cohort, previous SRT status, age group and overall based on the safety population. .

Pre-treatment AEs are any AEs that occur from the time the patient has signed informed consent until prior to the first study drug infusion.

Treatment-emergent adverse events (TEAEs) will be defined as those events that occurred or worsened in severity after first treatment with Replagal AF until 30 days after the last dose.

Infusion-related reactions (IRRs) will be defined as an AE that 1) begins either during or within 12 hours after the start of the infusion and 2) is judged as possibly or probably

related to study drug. AEs that are considered IRRs will be noted as such in the appropriate field on the CRF.

A serious AE (SAE) is any AE occurring at any dose that results in any of the following outcomes:

- Death
- Is life-threatening
- Require hospitalization
- Requires prolongation of existing hospitalization
- A persistent or significant disability or incapacity
- A congenital anomaly or birth defect

Important medical events that may not result in death, be life-threatening, or require hospitalization may be considered an SAE when, based upon appropriate medical judgment, they may jeopardize the patient and may require medical or surgical intervention to prevent one of the outcomes listed in this definition.

TEAEs will be summarized by system organ class (SOC) and preferred term (PT). The total number of TEAEs by SOC and PT, as well as the number and proportion of patients experiencing a TEAE will be tabulated; a patient will be counted only once within each SOC and PT. TEAEs by SOC and PT will be tabulated by severity. In the case of multiple occurrences of the same TEAE (at the PT level) in an individual patient, the TEAE that is classified as the most severe (i.e., maximum severity) will be identified for the analysis by severity. In addition, TEAEs by SOC and PT will be tabulated by relationship to study drug by reporting the episode with the closest relationship to study drug.

The number and percentage of patients reporting IRRs will be tabulated for any IRR, and by SOC and PT by cohort, previous SRT status, age group, sex and overall based on the safety population. IRRs by SOC and PT will be tabulated by severity and cohort, by serious and cohort, and by closest relationship. In addition, the number and percentage of patients with at least one, and no IRRs will be tabulated by anti-drug antibody (ADA) status and neutralizing antibody (NAb) status status.

The number and percentage of patients reporting SAEs will be tabulated for any SAE, and by SOC and PT by cohort, previous SRT status, age group, sex and overall based on the safety population. In addition, SAEs by SOC and PT will be tabulated by severity and relationship by cohort, separately.

The number and percentage of patients reporting TEAEs that led to permanent discontinuation will be tabulated for any TEAE, and by SOC and PT by cohort, previous ERT status, age groups and overall.

Separate data listings will be presented showing all SAEs, deaths, and TEAEs leading to treatment discontinuation.

All AEs will be listed by patient for the safety population and those AEs considered to be treatment-emergent, as well as IRRs will be flagged as such.

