1.3 Previous Human Experience

Clinical studies of agalsidase alfa have been conducted in the United States (US), United Kingdom (UK), Canada, Australia, Europe, Brazil, and Japan.

The clinical development program has included 3 placebo-controlled clinical studies of 6-month dosing duration in adults (TKT003, TKT005, TKT010) and open-label maintenance studies for patients continuing from these and other studies (TKT006, TKT007, TKT011, TKT013, and TKT015).

Additionally, a study in female patients (TKT014), a study in dialysis and renal transplant patients (TKT019), and a single-center, open-label, compassionate use study (TKT012) have also been performed. Three completed studies have been conducted in children (TKT023, TKT029, and TKT5S001). An additional study (TKT028) was conducted in patients with left ventricular hypertrophy. Other completed studies include REP001a, a Phase 4 study of alternative dosing regimens for Replagal in Canadian patients with Fabry disease; HGT-REP-059, a treatment protocol to provide access to Replagal for patients with Fabry disease in the US; HGT-REP-082, a comparability study between Replagal produced from agalsidase alfa manufactured by 2 different processes in Canada; HGT-REP-060, an open-label extension study for TKT028; and HGT-REP-084, a study of treatment-naïve children using Replagal manufactured using the bioreactor process (Replagal AF).

In total, 514 adults and 67 children have received Replagal in completed Shire-sponsored studies. Long-term safety experience demonstrates that Replagal therapy has been generally well tolerated in clinical studies, as well as in commercial and compassionate use.

Additional details of these clinical studies are available in the Investigator Brochure.

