5 STATISTICAL ANALYSIS

5.1 General Methodology

All analysis will be performed by the Biometrics Department, Shire HGT using SAS[®] Software version 9.3 or higher (SAS institute, Cary, NC, USA). All study data will be presented in by-patient data listings.

No formal statistical tests will be conducted. Tabular summaries of patient baseline demographic and clinical characteristics, patient disposition, medical history, vital signs, AEs, anti-agalsidase alfa antibody, and infusion information will be produced for the safety population. The safety population includes all patients who receive at least one full or partial infusion of Replagal. Continuous data collected prior to receiving study drug and at subsequent visits will be summarized using descriptive statistics (n, mean, median, minimum, maximum, and standard deviation). Categorical data will be summarized as frequencies and percentages. All data summaries will be presented for each cohort and overall, as appropriate, unless otherwise indicated

Cohort:

Cohort is defined as:

- Cohort 1: Patients from CFDI and receiving Replagal on EOW regimen
- Cohort 2: Patients who participated in REP001a and receiving Replagal on weekly regimen

Data Derivations:

The following key derived and computed variables have been initially identified. It is expected that additional variables may be required. The SAP will not be amended for additional variables. All derived and computed variables, including additional variables later identified, will be documented in the “Define Document,” and also in the SAS analysis dataset creation programs. The following are anticipated data derivations:

- *Screening period:* Within 6 months prior to first dose
- *Pre-treatment period:* Prior to first study drug infusion
- *Day 1:* Day of first study drug infusion
- *Date of Enrollment (entry):* Date informed consent is signed
- *Baseline:* Last valid non-missing assessment made prior to the first study drug infusion.
- *Change from Baseline:* Post-baseline value – Baseline Value

- *% Change from Baseline:* $\{(Change\ from\ Baseline / Baseline) * 100\}$
- *Change from Pre-infusion:* Value immediately after infusion – value immediately before infusion.
- *% Change from Pre-infusion:* $\{(Change\ from\ pre-infusion / pre-infusion) * 100\}$
- *Age:* integer of $\{(date\ of\ informed\ consent - date\ of\ birth) / 365.25\}$
- *Duration of study drug exposure:* (Date of last infusion – date of first infusion)+1

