- *Descriptive statistics:* n, mean, standard deviation (SD), median, minimum (min), and maximum (max)

Handling of Outliers:

For analysis purposes an outlier is defined to be an observed value which is known to be the result of an obvious error, or an observed value beyond medical reasoning. No outliers will be excluded from any analyses. The analysis may be repeated, however, by excluding any potential outliers (i.e. a sensitivity analysis performed).

Missing Dates for Adverse Events:

For partial AE dates, the non-missing parts of the partial dates will be used to determine if an AE occurred prior to the first dose of Replagal. Unless the non-missing parts are *unambiguously* before or after the first Replagal, it will always be assumed that the AE occurred after the first Replagal dose.

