5.6.3 Subset Analyses

Although no subgroup analysis is explicitly indicated in the study protocol, subgroup analyses by sex group, age group, previous ERT status, anti-drug antibody (ADA) status and neutralizing antibody (NAb) status will be performed, as applicable. Subgroups of age group, previous ERT status, ADA status and NAb status are defined as:

Age group (years) is defined as:

- <18
- ≥18

Previous ERT status is defined as:

- Previously on Fabrazyme (switched)
- Previously on RB Replagal
- Treatment-Naïve
- Other (including the patients who were previously on Fabrazyme and Replagal, on Replagal RB and Replagal AF, and whose ERT status is unknown)

ADA status is defined as:

- Positive: At least one positive test for ADA during the study evaluation period
- Negative: No positive test for ADA during the study evaluation period

NAb status is defined as:

- Positive: At least one positive test for NAb during the study evaluation period
- Negative: No positive test for NAb during the study evaluation period

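### The TEAE window opens at first Replagal AF treatment, so in patients given AF before this study an event between consent and first study infusion fits both AE classes

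*SAP*

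**What the plan says.** SAP 5.7.1 splits adverse events into two classes in consecutive sentences. Pre-treatment AEs are "any AEs that occur from the time the patient has signed informed consent until prior to the first study drug infusion". TEAEs are those that "occurred or worsened in severity after first treatment with Replagal AF until 30 days after the last dose". The first class closes at the first infusion in this study. The second opens at the first AF treatment, with no mention of this study.

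The other time anchors in SAP 5.1 follow the first form. Day 1 is the "Day of first study drug infusion" and Baseline is the "Last valid non-missing assessment made prior to the first study drug infusion".

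The partial-date rule in SAP 5.1 uses a third term. The known parts of a date "will be used to determine if an AE occurred prior to the first dose of Replagal", and when they do not settle the order, "it will always be assumed that the AE occurred after the first Replagal dose".

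SAP 5.6.3 defines previous-ERT groups. Its Other group includes patients who were previously "on Replagal RB and Replagal AF", so some participants are expected to arrive with earlier AF exposure.

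**The concern.** Study drug here is Replagal AF (Protocol synopsis and section 1.5; SAP 1.2). For most patients the first AF treatment is therefore the first study infusion, and the two classes meet without a gap or overlap. For a patient who had AF before this study, the TEAE window is already open at consent. An event in the interval before the first study infusion is then both pre-treatment and treatment-emergent, and the SAP gives no order of precedence.

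Safety is the only endpoint (SAP 4.2). The TEAE flag feeds the tables by system organ class, preferred term, severity and relationship, the discontinuation table, and the flags in the AE listing. The AE tables are also split by previous ERT status, which is the variable that decides who is exposed to the overlap. Two programmers working from the same text could produce different counts for these patients.

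**Working it through.** The point concerns definitions, and the plan gives no figure for it. The check applies each anchor to one event.

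**Inputs from the documents**
- AE observation starts at informed consent (Protocol 6.10.4.1), so only events after consent are in question.
- The pre-treatment class runs from consent to just before the first study infusion (SAP 5.7.1).
- The TEAE class, read literally, starts at the first AF treatment (SAP 5.7.1).
- Previous-ERT groups are those in SAP 5.6.3.

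**Illustrative dates (assumed)**
Consent is 10 January 2011, AE onset 25 January 2011 and first study infusion 20 February 2011. Where there was earlier Replagal, the first roller-bottle (RB) dose was 1 January 2006. Where there was earlier AF, it began on 1 March 2010.

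| Previous ERT | First AF treatment | First Replagal of any kind | Pre-treatment AE? | TEAE on the literal text? |
|---|---|---|---|---|
| None, or Fabrazyme only | 20 Feb 2011 | 20 Feb 2011 | Yes | No |
| Replagal RB only | 20 Feb 2011 | 1 Jan 2006 | Yes | No |
| Replagal RB and AF | 1 Mar 2010 | 1 Jan 2006 | Yes | Yes |

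Only the last row is in both classes. The result does not depend on the dates chosen, provided that AF began before AE onset and the event falls between consent and the first study infusion.

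**Partial dates**
The RB-only row would also go wrong if the first Replagal dose in SAP 5.1 meant the first in the patient's lifetime: an incomplete date that clearly precedes the first study infusion would still fall after the 2006 dose. Other sections show how the documents use the phrase. Protocol 6.1 (eligibility), 6.7 (blood tests) and 6.8 (antibodies), and SAP 5.7.2 and 5.7.5, all time procedures against the first Replagal dose and must mean the first dose in this study. Otherwise screening would be impossible for patients already treated with Replagal. On that usage the partial-date rule gives the right answer, and only its wording differs from the Day 1 definition.

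**The case against.** The strongest reply is that the SAP uses Replagal AF as a name for study drug. SAP 5.6 summarises duration of exposure to Replagal AF, while SAP 5.1 computes exposure duration from first to last infusion. The sentence just before the TEAE definition places events up to the first study infusion in the pre-treatment class. Read in sequence, the intent is probably pre-treatment first and treatment-emergent afterwards. That is fair as a reading of intent, and it is why the text supports only that such events can be counted as TEAEs, not that they will be. It does not remove the overlap, because SAP 5.6.3 itself uses AF for treatment received before this study.

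A second reply is that the consequences are limited. The study is descriptive with no formal tests, and all AEs are listed by patient with TEAEs flagged, so a misflag could be seen. The schedules of events mark no AE assessment in the pre-dose column, although observation formally starts at consent. The affected patients also sit in a mixed Other group, so the RB and Fabrazyme rows of the tables are not distorted when dates are complete. All of this stands, and it keeps the point minor.

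A reader might go further in three ways that the documents do not support.
- That all previously treated patients are affected. The table under working shows otherwise.
- That the partial-date rule misclassifies prior-RB patients. That needs a lifetime reading which the documents' own usage contradicts. Sending ambiguous dates to the post-dose side is a conservative choice and not a fault.
- That many AF-treated patients came from HGT-REP-082, described in Protocol 1.3 as "a comparability study between Replagal produced from agalsidase alfa manufactured by 2 different processes in Canada". It is a plausible source of earlier AF exposure, but nothing says that any of its patients entered this study.

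**Conclusion.** The inconsistency is real and narrow. For patients who received Replagal AF before this study, an AE between consent and first study infusion meets both definitions, and the SAP does not say which applies. Patients with only RB or Fabrazyme behind them are unaffected when dates are complete.

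The size cannot be computed. The documents give no number of prior-AF patients, no AE rate and no consent-to-dose interval. It is tempting to use the 6-month screening window with an assumed rate. With P(at least one event) = 1 − exp(−rate × time) and assumed rates of 1 to 5 AEs per patient-year:
- 6 months: 1 − exp(−0.5) = 39% to 1 − exp(−2.5) = 92% of prior-AF patients.
- 14 days: 1 − exp(−14/365.25) = 4% to 1 − exp(−5 × 14/365.25) = 17%.

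The answer is driven by the assumed gap. Six months is an outer limit for screening data, set to fit the CFDI visit schedule (SAP 3.2), and a protocol meant to keep supply uninterrupted (Protocol 1.5) makes long untreated gaps unlikely. None of these percentages is an estimate for this trial. The effect on the tables is probably small, and the severity is minor.

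**What to change.** In SAP 5.7.1, define TEAEs as events with onset, or an increase in severity, on or after the first study drug infusion in HGT-REP-081 and up to 30 days past the last study infusion. Pre-treatment AEs and TEAEs then exclude each other, except that a pre-treatment event which worsens after that infusion becomes treatment-emergent.

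In SAP 5.1, use the same term in the partial-date rule in place of the first Replagal dose. Keep the default that ambiguous dates count as after it.

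The cost is two wording changes before database lock. No new data are needed, nothing changes for patients without earlier AF when dates are complete, and there is no downside. As SAP 7.3 says the 2015 interim analysis included TEAEs, a line in the study report stating which anchor was used there would let the two sets of counts be compared.

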6.10.4 Procedures for Recording and Reporting Adverse Events

6.10.4.1 Adverse Event Monitoring and Period of Observation

Adverse events will be monitored continuously throughout the study.

For the purposes of this study, the period of observation extends from the time at which the patient, the patient's parent(s), or the patient's legally authorized representative gives informed consent until the patient's final evaluation of the study. For safety purposes, the final evaluation will be defined as the follow-up evaluation performed approximately 30 days after the last dose for patients who complete the study.

If the investigator considers it necessary to report an AE in a study patient after the end of the safety observation period, he or she should contact the sponsor to determine how the AE should be documented and reported.

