7.5 Adverse Events and Other Safety Assessments

Adverse event tabular summaries will be based on all treatment-emergent AEs recorded; AEs will be coded using the Medical Dictionary for Regulatory Activities coding dictionary.

Adverse events will be summarized by system organ class (SOC) and preferred term (PT). The total number of AEs by SOC and PT, as well as the number and proportion of patients experiencing an AE, will be tabulated by cohort; a patient will be counted only once within each SOC and PT. Adverse events by SOC and PT will be tabulated by cohort and severity. In the case of multiple occurrences of the same AEs (at the preferred term level) in an individual patient, the AE that is classified as the most severe (ie, maximum severity) will be identified for the analysis by severity. In addition, AEs by SOC and PT will be tabulated by cohort and relationship to study drug by reporting the episode with the closest relationship to study drug.

The number and percentage of patients reporting SAEs will be presented by cohort, SOC, and PT; in addition, an SAE listing will be presented.

The number and percentage of patients reporting an infusion-related reaction will be presented by cohort, SOC, and PT. An infusion-related reaction is defined as an AE that: (1) begins either during or within 12 hours after the start of the infusion and (2) is judged by the investigator to be possibly or probably related to study drug.

The number and proportion of patients experiencing an AE(s) that led to permanent discontinuation will be summarized by cohort, SOC, and PT. Furthermore, a listing of all patients who permanently discontinued due to an AE(s) will be provided.

Furthermore, safety will be evaluated by assessing vital signs and blood tests. Data for vital signs and blood tests will be listed for each patient and abnormal values will be flagged. Shift tables from baseline to last visit may be presented for vital signs, and a summary table may be presented for blood tests.

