5.6 Treatment Compliance and Extent of Exposure

Treatment compliance and extent of exposure will be summarized by cohort, previous ERT status and overall based on the safety population. The number of infusions initiated, missed (uninitiated), partial, and complete, average infusion time (in minutes) initiated and completed, duration of exposure to Replagal AF both in days and weeks, and cumulative dose of study drug taken will be summarized using descriptive statistics.

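### An AE that starts more than 30 days after the final infusion and ends treatment is left out of the SAP's permanent-discontinuation table and listing

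*SAP*

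**What the plan says.** SAP 5.7.1 defines a treatment-emergent AE (TEAE) as one that "occurred or worsened in severity after first treatment with Replagal AF until 30 days after the last dose". It contains no rule for treatment gaps, and the Protocol has no TEAE definition of its own.

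The same SAP section limits the discontinuation outputs to TEAEs. For the table: "The number and percentage of patients reporting TEAEs that led to permanent discontinuation will be tabulated for any TEAE". For the listings: "Separate data listings will be presented showing all SAEs, deaths, and TEAEs leading to treatment discontinuation".

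Protocol 7.5 plans the corresponding summary in terms of AEs: "The number and proportion of patients experiencing an AE(s) that led to permanent discontinuation will be summarized by cohort, SOC, and PT". It then promises a listing of all patients who stopped permanently because of an AE. However, 7.5 opens by basing AE tables in general on treatment-emergent events.

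Three other places bear on the point:
- Protocol 6.10.4.1: "Adverse events will be monitored continuously throughout the study". The final safety evaluation is "the follow-up evaluation performed approximately 30 days after the last dose for patients who complete the study".
- SAP 5.6 expects missed doses and counts them: "The number of infusions initiated, missed (uninitiated), partial, and complete".
- SAP 5.1 computes exposure duration from "Date of last infusion – date of first infusion)+1", without subtracting gaps.

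**The concern.** A discontinuation table should show which AEs ended treatment. Here a cut-off designed for a different purpose decides whether such an AE may appear. Once a patient has been off drug for more than 30 days but remains on study, a new AE is a TEAE if infusions resume. It is not a TEAE if they never do. For these late-onset events, the one that ended treatment is therefore the one left out.

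Safety is the only objective of the study, and AEs leading to permanent discontinuation are one of its main outputs. An omission would make the reported rate too favourable. It could also make the disposition table, which gives the primary reason for stopping without a TEAE limit (SAP 5.3), disagree with the AE table without explanation.

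**Working it through.** The plan states no figure on this point, so there is none to reproduce. The check applies the rule as written and then works out when a gap passes 30 days.

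**1. Which infusion is the last dose?** The exposure formula in SAP 5.1 uses the last infusion as a single end point, so the natural reading is the final infusion given (reading A). The SAP does not spell this out, so the most recent infusion before the AE (reading B) is checked as well.

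**2. Apply the rule.** An AE is a TEAE if first infusion ≤ onset ≤ last dose + 30 days. Onset is counted from the infusion before the AE, and resumption is set at day 70 for illustration.

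| Onset | A, dosing resumes | A, never resumes | B, either case |
|---|---|---|---|
| Day 10, 29 or 30 | TEAE | TEAE | TEAE |
| Day 31, 45 or 60 | TEAE | not TEAE | not TEAE |

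Under A, the later course of treatment decides the label from day 31 on. Under either reading, an AE starting on day 31 or later with no further infusion is not a TEAE, so it cannot enter the discontinuation table or listing.

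**3. Can a patient be on study at that point?** Neither document sets a gap length or a number of missed infusions that ends participation. Observation runs until the final evaluation, so AEs during a gap are recorded.

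**4. How many missed infusions pass 30 days?** Nominal gap after k consecutive missed infusions = interval × (k + 1). At the visit-window limits (first infusion early, next one late), add twice the window, which is 5 days for every other week and 2 days for weekly.
- Every other week, k = 2: 14 × 3 = 42 days, 12 beyond day 30. At the limits k = 1 suffices: 28 + 10 = 38 days.
- Weekly, k = 4: 7 × 5 = 35 days, 5 beyond day 30. At the limits k = 3 suffices: 28 + 4 = 32 days.

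**5. Where does the omitted AE still appear?**
- All-AE listing (SAP 5.7.1): yes, without the TEAE flag.
- Disposition (SAP 5.3): possibly, as the primary reason, without system organ class or preferred term.
- SAE table and the SAE and death listings (SAP 5.7.1): yes if serious or fatal, because these are not worded as limited to TEAEs.
- TEAE tables, discontinuation table, discontinuation listing: no.

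A non-serious AE of this kind is therefore in no summary table by system organ class and preferred term.

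**6. Size per patient.** With the planned minimum of 60 patients, 1/60 = 1.7 percentage points; with the maximum of 200, 1/200 = 0.5 points.

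**The case against.** The 30-day limit is a coherent choice. It matches the follow-up about 30 days after the last dose in Protocol 6.10.4.1, 6.13 and the schedules of events. An AE that itself stops dosing usually starts close to the last infusion, so it falls inside the window and is counted. The omission needs a patient who is off drug for more than 30 days for some other reason and still on study, and who then has an AE recorded as the cause of permanent discontinuation. Protocol 6.13 narrows this further, because a patient who refuses treatment is to be withdrawn. The TEAE basis of the table also follows the opening sentence of Protocol 7.5, and the study is descriptive, with no formal tests. All of this stands, and it limits the size of the problem. It does not explain why a discontinuation output needs the 30-day cut, or why the SAP listing is narrower than the one promised in 7.5.

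A reader might infer more than the documents support:
- *That the worst outcomes vanish.* They do not: serious and fatal events stay in the SAE table and listings.
- *That no AE ending treatment during a gap can be tabulated.* One starting within 30 days of the last infusion is counted. Under reading A, so is a later one followed by at least one more infusion before stopping.
- *That the TEAE window should be tied to the most recent infusion.* This recovers none of the omitted events, since day 35 after the final infusion is still outside. Under reading A it also removes gap events that the SAP now counts, so TEAE counts could only stay equal or fall.
- *That the regimens are compared unfairly.* The limit is reached after fewer missed infusions every other week, but no formal cohort comparison is planned.

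**Conclusion.** The point holds for the permanent-discontinuation table and listing. Any AE starting more than 30 days after the final infusion and recorded as ending treatment is left out of both, under either reading of last dose. If such an event occurs, it can only lower the reported discontinuation rate.

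The number of such events cannot be computed, because the documents give no frequency of gaps over 30 days; it is probably small and may be zero. The conclusion assumes that AEs in a gap are recorded, as Protocol 6.10.4.1 requires, and that the SAE outputs are produced as worded, without a TEAE restriction. The point does not extend to the TEAE definition as a whole. The change is worth making because it is cheap and brings the listing back to what the Protocol promises.

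**What to change.** In SAP 5.7.1:
- Base the permanent-discontinuation table and listing on all AEs with onset or worsening after the first study infusion, through study exit, that are recorded as leading to permanent discontinuation, whether or not they fall inside the 30-day window.
- Footnote the number of these that started more than 30 days after the last infusion.
- Leave the general TEAE window unchanged.

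In SAP 6.3, record that this table departs from the treatment-emergent basis stated for AE tables in Protocol 7.5, and that the listing now matches the one promised there.

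The cost is SAP wording and a changed filter in two outputs; no new data are needed. The discontinuation rate may be slightly less favourable. The table would no longer be a strict subset of the TEAE table, which the footnote makes visible.

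### Safety events are tabulated as patients ever affected over open-ended, unequal follow-up, with no exposure-adjusted or fixed-window measure; the infusion-reaction by antibody-status table is the most exposed

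*SAP*

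**What the plan says.** For three event classes SAP 5.7.1 names patients as the unit of the main tables:

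- Serious adverse events (SAEs): "The number and percentage of patients reporting SAEs will be tabulated for any SAE, and by SOC and PT by cohort, previous SRT status".
- IRRs: "The number and percentage of patients reporting IRRs will be tabulated for any IRR, and by SOC and PT by cohort, previous SRT status".
- Discontinuations: "The number and percentage of patients reporting TEAEs that led to permanent discontinuation will be tabulated for any TEAE".

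(I read SRT in the first two as a slip for ERT.) Treatment-emergent adverse events (TEAEs) also get event counts: "The total number of TEAEs by SOC and PT, as well as the number and proportion of patients experiencing a TEAE will be tabulated". Protocol 7.5 plans no rate either.

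The TEAE window runs "after first treatment with Replagal AF until 30 days after the last dose", so its length is specific to each patient. SAP 3.1 lets treatment continue until commercial availability or discontinuation, with no fixed end.

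IRRs are also crossed with antibody status: "the number and percentage of patients with at least one, and no IRRs will be tabulated by anti-drug antibody (ADA) status", and by NAb status. SAP 5.6.3 defines the grouping over the whole study: "Positive: At least one positive test for ADA during the study evaluation period". NAb status is defined in the same way.

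Exposure has its own summary in SAP 5.6: "Treatment compliance and extent of exposure will be summarized by cohort, previous ERT status and overall based on the safety population".

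**The concern.** Safety is the study's only objective, and these are its main tables. A percentage of patients ever affected, over follow-up of unequal length, mixes risk with time observed and number of infusions. It has no time unit and is hard to compare between groups or with other sources.

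The IRR by ADA/NAb table is the most exposed because row and column both accumulate. A patient followed for longer has more antibody tests in which to turn positive and more infusions in which to react. Longer-followed patients therefore collect in the cell that is both positive and reacting. A reader could take the resulting gap for antibody-driven risk.

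**Working it through.** **The plan's own figure.** SAP 3.6 states at least a 95% chance of seeing one or more events of 5% frequency in 60 patients: 1 − 0.95^60 = 95.4%, which agrees. The 5% carries no time unit.

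**What can be rebuilt from the planned tables.**
- TEAE totals (SAP 5.7.1) with the exposure summary (SAP 5.6) would give a crude TEAE rate by cohort, by previous ERT status and overall. It would be approximate: SAP 5.1 counts exposure from first to last infusion, without the 30-day tail of the TEAE window.
- SAE and IRR rates could not be rebuilt in this way, because no event totals are specified for them.
- No exposure summary is clearly planned by age, sex or ADA/NAb status. SAP 5.6.3 says subgroup analyses are done as applicable, and SAP 7.6 speaks of selected analyses.
- The 24-month rule in SAP 7.3 selected patients for the 2015 interim analysis. It is not a window for the final analysis.

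**Illustration for the ADA table.** The documents give no hazards and no follow-up distribution, so all of these are assumed. Let ADA conversion (hazard μ) and first IRR (hazard λ) be independent, with

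a(T) = 1 − exp(−μT), i(T) = 1 − exp(−λT).

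Then, averaging over the follow-up times T:

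P(IRR | ever ADA+) = Σ a·i / Σ a; P(IRR | never ADA+) = Σ (1 − a)·i / Σ (1 − a).

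With μ = λ = 0.1 per year and half the patients at T = 1, half at T = 5, a = i = 0.0952 and 0.3935:

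- ADA+: (0.0952² + 0.3935²) / (0.0952 + 0.3935) = 33.5%
- ADA−: (0.0952 × 0.9048 + 0.3935 × 0.6065) / (0.9048 + 0.6065) = 21.5%

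The false gap is 12.0 points. Mean follow-up is 4.22 years in ADA+ and 2.61 years in ADA−.

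| Assumed follow-up (hazards 0.1) | ADA+ | ADA− | Gap, points |
|---|---|---|---|
| Half 1, half 5 years | 33.5% | 21.5% | 12.0 |
| Continuous uniform, 1 to 5 years | 28.3% | 24.4% | 3.9 |
| Half 2, half 4 years | 27.7% | 24.8% | 2.9 |
| 3 years for all | 25.9% | 25.9% | 0 |

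Spreading patients equally over exactly 1, 2, 3, 4 and 5 years gives 29.6% vs 23.7%, or 5.9 points. With each hazard varied over 0.05, 0.1 and 0.2, the gap is 6.4 to 21.1 points (1/5 years) or 1.6 to 5.0 points (2/4 years).

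**Patients already positive at entry.** Replace a(T) by p + (1 − p)·a(T) in the 1/5-year case. ADA− stays at 21.49%. With p = 30%, ADA+ is 27.74%, a gap of 6.25 (about 6.3) points. With p = 50%, ADA+ is 26.22%, a gap of 4.7 points.

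**Does a simple rate by ever-positive status cure it?** Only if IRR risk is constant over time; then the 1/5-year case gives 10.0 per 100 patient-years in both groups. Now put all IRR risk in year 1 (assumed hazard 0.3):
- Percentages: 1 − exp(−0.3) = 25.9% in both groups, so no artefact.
- Rates: 0.3 / 4.22 = 7.1 vs 0.3 / 2.61 = 11.5 per 100 patient-years, a false protective effect of ADA.
- With 0.3 in year 1 and 0.02 per year after that: percentages 30.5% vs 28.2%, rates 8.6 vs 12.7.

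**Dosing frequency.** At an assumed 0.25% IRR risk per infusion, one year gives 1 − 0.9975^26 = 6.3% every other week and 1 − 0.9975^52 = 12.2% weekly.

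**Competing events.** At assumed hazards of 0.10 (discontinuation TEAE) and 0.20 (other stopping) per year, the 12-month figure is 1 − exp(−0.10) = 9.5% by 1 − Kaplan-Meier, against (0.10/0.30)(1 − exp(−0.30)) = 8.6% as cumulative incidence.

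**The case against.** The strongest case against is as follows.

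- **The study is descriptive.** There are no tests, the objective is to observe safety, and patient percentages follow the protocol and fit the sample-size rationale. This stands as far as error control goes. But without tests the reader relies wholly on the displayed percentages, so what they measure matters.
- **The data will be available.** SAP 5.1 lists all data by patient, SAP 5.7.1 lists AEs with IRR flags, SAP 5.7.5 lists antibody results, and Protocol 7.3 lists infusions. SAP 1.2 allows further safety exploration. A reader might infer that rates cannot be obtained at all; that would be wrong. What stands is that no planned table shows them.
- **The unit is not always explicit.** The breakdowns of IRRs and SAEs by severity and relationship do not say whether patients or events are counted. A reader might infer that these classes are counted as patients everywhere; the text fixes that only for the tables quoted above.
- **The size rests on assumptions.** This stands. The 12-point figure needs a sharp 1/5-year split and nobody positive at entry. Yet SAP 5.6.3 provides for patients previously on Fabrazyme or roller-bottle Replagal, and Cohort 2 comes from an earlier Replagal study.
- **A plain rate can mislead more than the percentage.** This also stands, as the year-1 example shows, and it shapes the fix.
- **The weekly versus every-other-week contrast is no defect.** Agreed. A reader might take a higher IRR percentage with weekly dosing for an artefact. At equal risk per infusion it is a real difference in annual risk, so both measures are informative.

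**Conclusion.** The omission is clear from the text: follow-up is open-ended and differs by patient, and no rate, per-infusion measure or fixed-window incidence is planned in either document. It should be corrected, because it affects how the study's only objective is read. No planned result is made invalid.

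The ADA/NAb table is the most exposed, but a reader might go further and infer that it will show a false association of some 12 points. The documents do not support that. Under assumed independent hazards of 0.1 per year the gap ranges from 12.0 points to zero according to follow-up. In the 1/5-year case it falls to 6.3 or 4.7 points with 30% or 50% positive at entry, and it vanishes if all IRR risk lies in year 1. Patients who stop early because of an IRR could reverse it. Nor do the documents support the inference that dividing by patient-years settles the matter, since that needs constant IRR risk. Rates would not make these non-randomised groups comparable in other respects.

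**What to change.** Keep the patient percentages and add to SAP 5.7.1, by cohort, previous ERT status and overall:

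- (a) Number of events and events per 100 patient-years for TEAEs and SAEs, with time from first infusion to last infusion + 30 days (or death or end of observation if earlier), so that the denominator matches the TEAE window.
- (b) IRRs per 100 infusions initiated, split into the first 12 months and later. Infusions are the right denominator because an IRR must begin within 12 hours of the start of one.
- (c) Cumulative incidence of a first TEAE, SAE and IRR in the first 12 months, with administrative end of follow-up as censoring and death as a competing event. For first IRR and for discontinuation TEAEs, also treat stopping treatment for other reasons as a competing event.

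For the ADA/NAb table, do not rely on an overall rate by ever-positive status. Classify each infusion by the patient's ADA/NAb status at the latest test before it, and show IRRs and infusions by that status, within the first 12 months and later.

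In the age and sex tables, print events, patient-years and number of infusions for each column.

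Cost: SAP wording and programming only, because infusion dates, AE dates and antibody results are already collected. The downsides are a modest number of extra descriptive tables, unstable rates in small groups (so show counts with them), and antibody status known only at biannual or annual tests.
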